## APPENDIX L SLIT-LAMP EXAM RATINGS

### A. Ratings of Aqueous Cells and Flare

For consistency across study sites, the SUN (Standardization of Uveitis Nomenclature) Working Group Grading Scheme is to be used for grading of anterior chamber cells and flare as reported in: Standardization of uveitis nomenclature for reporting clinical data. Results of The First International Workshop; The standardization of uveitis nomenclature (SUN) working group. Am J Ophthalmol 2005;140:509-516.

#### CELLS

Grade	Cells in Field (Field is a 1x1 mm slit beam)
0	<1
0.5+	1 - 5
1+	6 - 15
2+	16 - 25
3+	26 - 50
4+	>50

#### FLARE

Grade	Description
0	None
1+	Faint
2+	Moderate (iris and lens details clear)
3+	Marked (iris and lens details hazy)
4+	Intense (fibrin or plastic aqueous)

### B. Ratings of Corneal Edema

Corneal edema should be classified according to the haziness of the epithelium, the number of microcysts observed, and the clouding of the stroma.

Amount	Grade	Description
None	0	Normal transparency: a. No epithelial or sub-epithelial haziness b. No microcysts c. No stromal cloudiness
Trace	+1	a. Barely discernible localized epithelial or sub-epithelial haziness, and/or b. 1 to 20 microcysts, and/or c. Barely discernible localized stromal cloudiness
Mild	+2	a. Faint but definite localized or generalized epithelial, sub-epithelial or stromal haziness/cloudiness, and/or b. 21-50 microcysts
Moderate	+3	a. Significant localized or generalized epithelial, sub-epithelial or stromal haziness/cloudiness and/or b. 51-100 microcysts
Severe	+4	a. Definite widespread epithelial or stromal cloudiness, giving dull glass appearance to cornea or numerous coalescent bullae (please note the number and location of bullae), and/or b. >100 microcysts or bullae, and/or c. Numerous striae (please note the number and location of striae or folds)

### C. Posterior Capsule Striae Grading Scale

The following five-point grading scale is to be used for rating striae in the posterior capsule:

Amount	Grade	Description
None	0	None
Trace	+1	One detectable, barely noticeable striae
Mild	+2	One or two prominent striae
Moderate	+3	Three or more prominent striae, but visibility of retina is not impacted
Severe	+4	Three or more prominent striae affecting visualization of retina

### D. Posterior Capsule Opacification Grading Scale

Below is the five-point grading scale to be used for PCO determination:

Amount	Grade	Description
None	0	Normal posterior capsule with no area of opacity. Red reflex bright.
Trace	+1	Some loss of transparency involving the posterior capsule. Red reflex fairly bright
Mild	+2	Mild loss of transparency with cloudiness extending through most of the posterior capsule. There may be a few Elschnig's pearls in the posterior capsule. Red reflex mildly diminished.
Moderate	+3	Moderate loss of transparency with difficulty visualizing the retina. There may be multiple Elschnig's pearls in the posterior capsule. Red reflex markedly diminished.
Severe	+4	Posterior capsule very opaque with inability to view the retina. The posterior capsule may have confluent Elschnig's pearls and fibrous scarring. Red reflex barely visible.

### E. IOL Glistenings

Use the following scale to grade IOL glistenings, using a slit beam 2.0 mm wide and 10.0 mm long:

Amount	Grade	Description
None	0	No glistenings visible
Rare	+0.5	<10 glistenings visible
Trace	+1	10-19 glistenings visible
Mild	+2	20-29 glistenings visible
Moderate	+3	30-39 glistenings visible
Severe	+4	≥40 glistenings visible

1 INTRODUCTION

This document summarizes the statistical methods to be implemented during the analysis of data for the TECNIS[®] Next-Generation IOLs, Models ZFR00 and ZYR00, clinical study (Protocol SUR-CAT-652-1001). This study will be a prospective, multicenter, subject/evaluator-masked, bilateral, randomized, clinical trial conducted at up to 14 sites. The two test lenses, TECNIS Model ZFR00 and Model ZYR00 IOLs, will be compared to the control lens, TECNIS Multifocal IOL, Model ZLB00, separately. Subjects are to be implanted with the same IOL in both eyes, the ZFR00 IOL, the ZYR00 IOL or the multifocal control IOL. Up to 260 subjects will be enrolled to achieve approximately 220 randomized and bilaterally-implanted subjects, resulting in approximately 195 evaluable subjects (65 in each IOL group) at 1 and 6 months.

The primary effectiveness endpoints for this study are mean (LogMAR) monocular, photopic, distance corrected intermediate visual acuity (DCIVA) at 66 cm. The primary safety endpoints are adverse event rates versus ISO 11979-7:2006/ Amd.1:2012(E) Safety and Performance Endpoint (SPE)¹ rates.

Other effectiveness endpoints include mean monocular and binocular diopters of defocus, monocular and binocular uncorrected and best corrected distance, uncorrected intermediate, uncorrected and distance corrected near, monocular and binocular 10% low-contrast distance corrected visual acuities, and questionnaire responses.

Additional safety endpoints include the proportion of first implanted eyes achieving 20/40 or better monocular photopic best corrected distance visual acuity vs. the ISO SPE rate, optical/visual symptoms, medical/lens findings, monocular and binocular best corrected distance contrast sensitivity and visual symptoms via PRO instrument.

The key study timeframe will be the 1-month postoperative visit, although data will be reviewed at other time points as well.

2 ANALYSIS POPULATIONS

2.1 ANALYSIS POPULATIONS

The analysis population will be the safety population, which includes all eyes implanted with either a test or control IOL(s) and with data available at the time of analysis (i.e., no data imputation). For bilateral testing and subject-based questionnaires, only subjects binocularly implanted with the same test lens or the same control lens will be included. If an eye or a subject is discontinued during the study, any available data prior to the study exit will be included in the analyses.

The primary analysis will be based on first-eye or binocular outcomes (as appropriate per effectiveness endpoints), unless stated otherwise. However, select data such as

medical/lens complications and adverse events will also be reported separately for second eyes. Binocular data will be reported for those who are implanted with the same IOL (test or control) in both eyes.

The two test lens, TECNIS Model ZFR00 and Model ZYR00 IOLs, will be compared to the TECNIS multifocal control IOL, Model ZLB00, separately and independently. All endpoint comparison analysis to the control lens will present in two separate tables as follows:

- ZFR00 vs. control
- ZYR00 vs. control

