#### JUSTIFICATION OF STUDY DESIGN

This study is being conducted to capture preliminary safety and effectiveness information on two design candidates, with the goal of selecting a final lens design. The prospective, multicenter, subject/evaluator-masked, bilateral, randomized study design was chosen to optimize comparison of visual outcomes between the Models ZFR00 and ZYR00 investigational IOLs and the Model ZLB00 control IOL, while minimizing the number of subjects by utilizing the same control group for statistical comparisons.

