#### INDICATIONS FOR INVESTIGATIONAL IOLS

The Model ZFR00 is currently indicated for primary implantation for the visual correction of aphakia, in adult patients with less than 1 diopter of preexisting corneal astigmatism, in whom a cataractous lens has been removed. The lens mitigates the effects of presbyopia; compared to a standard multifocal IOL, the lens is intended to provide improved intermediate visual acuity, while maintaining comparable near and distance visual acuity. The Model ZFR00 IOL is intended for placement in the capsular bag only.

The Model ZYR00 is currently indicated for primary implantation for the visual correction of aphakia, in adult patients with less than 1 diopter of preexisting corneal astigmatism,

in whom a cataractous lens has been removed. The lens mitigates the effects of presbyopia; compared to a standard multifocal IOL, the lens is intended to provide improved intermediate visual acuity, while maintaining comparable near and distance visual acuity. The Model ZYR00 IOL is intended for placement in the capsular bag only.

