#### PUPIL SIZE

Photopic (without glare), and mesopic with and without glare pupil sizes will be measured postoperatively during the study. For consistency, the same method of measurement should be used throughout the study.

Photopic pupil size measurements are to be performed under the same lighting conditions at which photopic distance visual acuity is tested. Pupil sizes under the other lighting conditions will be measured during the contrast sensitivity testing procedures. Instructions for measuring pupil size are detailed in **Appendix J**.

DISTANCE CONTRAST SENSITIVITY TESTING (MASKED PROCEDURE)

Best corrected distance contrast sensitivity will be tested under mesopic with and without glare and photopic without glare conditions using the M&S System for sine-wave gratings at 1.5, 3.0, 6.0, 12.0 cycles per degree (cpd) (mesopic and mesopic with glare) and 3.0, 6.0, 12.0 and 18.0 cpd (photopic without glare). **The test distance is 8 feet (2.5 meters).** Best corrected distance contrast sensitivity is to be performed with a +0.12 D refractive adjustment to the sphere of the manifest refraction. Detailed instructions for contrast sensitivity testing are provided in **Appendix K**.

The following contrast sensitivity measurements are to be performed per the visit schedule in **Appendix A**:

Contrast Sensitivity Test	Test Distance	Spatial Frequency	Type of Testing	Refraction Adjustment
Photopic (85 cd/m  ) without glare	2.5 m	3, 6, 12 and 18 cpd	Monocular Binocular	+0.12 D added to ETDRS sphere Rx
Mesopic (3 cd/m  ) without glare	2.5 m	1.5, 3, 6 and 12 cpd	Monocular Binocular	+0.12 D added to ETDRS sphere Rx
Mesopic (3 cd/m  ) with glare	2.5 m	1.5, 3, 6 and 12 cpd	Monocular Binocular	+0.12 D added to ETDRS sphere Rx

BIOMICROSCOPIC SLIT-LAMP EXAM

A biomicroscopic slit-lamp exam must be performed at each postoperative visit to determine the presence or absence of any medical or lens findings, complications or adverse events. IOL decentration and tilt are to be determined subjectively. The center of the lens relative to the pupil can be used to determine IOL decentration, with the diffractive rings used as a guide to locate the center of the IOL. Note that the pupil center may not always be aligned with the visual axis of the eye; therefore, the investigator should consider deviations in pupil center from visual axis when reporting IOL decentration.

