### 17. RISK ANALYSIS

#### POTENTIAL RISKS AND RISK MANAGEMENT

##### *RISKS OF THE TECNIS NEXT-GENERATION IOLS, MODELS ZFR00 AND ZYR00*

The TECNIS Models ZFR00 and ZYR00 IOLs are designed to provide far, intermediate and near vision; however, glasses may still be needed to improve distance vision and/or to have useful vision for intermediate or near tasks. Visual symptoms, particularly dysphotopsias such as halos, night glare, starbursts, etc., are expected to be comparable to or less than with a standard multifocal IOL. Dysphotopsias may become less noticeable over time; however, the IOL may be removed if necessary. There may be a reduction in contrast sensitivity under certain conditions compared to a monofocal lens although contrast sensitivity is expected to be in between that of the TECNIS Symphony IOL and TECNIS Multifocal IOLs. Due to the diffractive optic design, the ability to perform some eye treatments (e.g., retinal photocoagulation) may be affected, and caution should be used when interpreting results of autorefractors or wavefront aberrometers that utilize infrared light, or when performing a duochrome test. These risks are not unlike other diffractive technology IOLs.

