## **20. STATISTICAL METHODS**

This section highlights the analyses to be performed for key study endpoints. The key study timeframe for all endpoints will be the 1-month postoperative visit, although data will be reviewed at other time points as well. TECNIS Models ZFR00 and ZYR00 will both be compared to the TECNIS Model ZLB00 control separately for all analyses. All data will be reported by IOL group.

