## **20.6 SAMPLE SIZE CALCULATIONS**

For the primary endpoint of distance corrected intermediate visual acuity, there is 90% power to detect a 1-line or greater difference in mean visual acuity between the investigational lens groups and the control group (assume one-sided testing with an alpha of 0.025 and standard deviation of 1.6 lines) with 65 subjects in each lens group.

For contrast sensitivity there is 80% power to detect a non-inferiority margin of 0.15 log units between the investigational lens groups and the control group (assume one-sided alpha=0.05 and standard deviation of 0.34) with 65 subjects in each lens group.

If the dropout rate is assumed at 10%, approximately 73 subjects will be implanted in each lens group to achieve a minimum of 65 subjects in each lens group at 1 and 6 months.

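### Selecting one of two lens designs is a stated goal, but no ZFR00-versus-ZYR00 difference or interval is prespecified; one exploratory SAP table would supply it

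*SAP*

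**What the plan says.** **Goal.** The justification in Protocol Section 4 says the study is to capture "preliminary safety and effectiveness information on two design candidates, with the goal of selecting a final lens design". It adds that subject numbers are kept down by "utilizing the same control group for statistical comparisons".

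**Comparisons planned.** Protocol Section 20 states that "TECNIS Models ZFR00 and ZYR00 will both be compared to the TECNIS Model ZLB00 control separately for all analyses". SAP 2.1 repeats this and says: "All endpoint comparison analysis to the control lens will present in two separate tables as follows". Two items follow, each a test lens against control. The Protocol synopsis and SAP 1 also describe separate comparisons with control. Neither document gives a ZFR00-minus-ZYR00 estimate, interval or test, or a rule for choosing the design. The general wording on comparisons between IOL groups (demographics, questionnaires) names no contrast between the two test lenses.

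**What is tabulated.** All data are reported by IOL group. SAP Appendix I puts ZFR00, ZYR00 and control in adjacent columns with N, mean, SD and an interval for each group.

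**Sample size.** Protocol 20.6 says that, with 65 per group, one-sided alpha 0.025 and an SD of 1.6 lines, "there is 90% power to detect a 1-line or greater difference in mean visual acuity between the investigational lens groups and the control group". SAP 8 gives the same figures but calls the primary endpoint distance corrected near acuity. SAP 5.2 sets its hypotheses on DCIVA, yet its success criterion names DCNVA.

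**The concern.** Success against control does not say which lens to take forward. If both lenses beat control, the primary tests leave the choice open. If only one does, it is tempting to read that as a difference between the lenses, and the tests do not measure that difference.

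Someone will therefore compare the two lens columns. Without a prespecified contrast, that comparison can be made on any of the many endpoints in Protocol 6.3, at 1 or 6 months, monocularly or binocularly, and with any interval. What is at stake is how disciplined the design choice is. The validity of either claim against control is not affected.

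**Working it through.** **Inputs.** 65 evaluable per group, SD 1.6 lines, one-sided alpha 0.025, target gain 1 line (Protocol 20.6, SAP 8). One line is 0.1 LogMAR (SAP 7.2). Log contrast sensitivity SD 0.34 (Protocol 20.6). The control group is shared (Protocol Section 4), so with equal group sizes the two test statistics have correlation 0.5.

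**1. The plan's own power figure.** SE of a difference = 1.6 × √(2/65) = 0.281 line. Noncentrality = 1/0.281 = 3.56, with 128 degrees of freedom and critical t = 1.979. Power by the noncentral t is 94.3% for each lens (94.6% by the normal approximation). The stated 90% would need 54 (normal) or 55 (t) per group. A figure of 90% does appear as the probability that both lenses succeed when each truly gains 1 line (90.0% by simulation), and also at one-sided 0.0125 (90.1%). The text does not say which was meant. Read per lens, which is the natural reading, 90% is a floor.

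**2. What the two control tests say about choosing a lens.** Simulation of two t-tests sharing a control group, one million runs or more per row:

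| True gains over control (lines) | Both succeed | Exactly one succeeds |
|---|---|---|
| 1 and 1 | 90.0% | 8.5% |
| 1 and 1.5 | 94% | – |
| 1 and 0.5 | 42% | 53% |
| 1 and 0.25 | – | 80% |
| 1 and 0 | – | 92% |
| 0.75 and 0.75 | 63% | 26% |
| 0.5 and 0.5 | 26% | 33% |

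A dash marks a figure not needed here. When both lenses gain at least 1 line, the tests usually do not separate them, even with a true half-line gap. When one lens gains much less, they often do. But a split result also occurs with identical lenses, in up to a third of trials in these rows. The documents give no expected gain per lens, so these rows are scenarios.

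**3. What a direct comparison would deliver.**
- DCIVA: SE 0.281 line; 95% half-width = 1.979 × 0.281 = 0.56 line (0.056 LogMAR).
- Two-sided 0.05 power: 94% for a 1-line difference, 76% for 0.75 line, 42% for 0.5 line.
- Probability that the observed difference favours the truly better lens: Φ(0.5/0.281) = 96% at a half-line difference and Φ(0.25/0.281) = 81% at a quarter line.
- Log contrast sensitivity: half-width = 1.979 × 0.34 × √(2/65) = 0.12 log unit for each condition.
- DCNVA and BCDVA: the documents give no SD. If it is also 1.6 lines, the half-width is again 0.56 line.

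**4. Number of intervals.** Protocol 10.7 tests contrast at four spatial frequencies in each of three lighting conditions: 4 + 4 + 4 = 12. With three acuities, 12 + 3 = 15.

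**The case against.** **The goal rests on one sentence.** Design selection appears only in the justification, which calls the information preliminary. The stated purpose, hypotheses and success criteria concern each lens against control or against ISO rates. This stands, and it is why the point is about supporting analysis only. A reader might infer that the primary tests are flawed or that the trial cannot serve its purpose. The documents do not support that, because each lens has its own clear hypothesis and criterion.

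**Most of the content is already there.** Appendix I gives the means and SDs from which the difference and its interval follow. This also stands. What is missing is the commitment in advance to endpoint, eye, visit and interval.

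**A table is not a selection rule.** Correct. Fifteen unadjusted intervals leave the decision with the sponsor, and no passage says that the choice will be made by counting significant tests. The 33% and 26% figures also assume gains below the 1-line design effect; at that effect the figure is 8.5%.

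**The endpoint list is a judgement.** It leaves out depth of focus, binocular outcomes and spectacle independence. The acuities follow the intended use shared by both lenses, under which "the lens is intended to provide improved intermediate visual acuity, while maintaining comparable near and distance visual acuity". Contrast sensitivity follows the risk section, where "contrast sensitivity is expected to be in between that of the TECNIS Symphony IOL and TECNIS Multifocal IOLs". The sponsor may reasonably add to the list before the data are seen. Visual symptoms also matter, but the documents do not give the PRVSQ response scale, so that contrast is best added once scoring is fixed.

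**The power wording.** A reader might infer from step 1 that the trial is underpowered or the sample size wrong. Neither follows. Power per lens exceeds the stated figure, and the contrast sensitivity calculation independently supports 65 per group (80.4% against a stated 80%). Nor does the shared control call for an adjustment: it is disclosed, the lenses are judged separately, and the probability of at least one false success when neither lens beats control is about 4.5%.

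**Conclusion.** The point holds as a cheap improvement. The plan names design selection as a goal and prespecifies no estimate of the difference between the two designs. The control tests are a poor substitute: if both lenses gain 1 line, both succeed in 90% of trials, and if both gain half a line, exactly one succeeds in 33%. One success and one failure is therefore not in itself evidence that the lenses differ.

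A direct estimate would be useful but imprecise, at about ±0.56 line for DCIVA. These figures assume the plan's SD of 1.6 lines, 65 evaluable per group and roughly normal data. They do not support a superiority claim between the lenses.

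The power statement is a minor matter of wording. The near-acuity labels in SAP 8 and SAP 5.2 are slips to correct, and the one in SAP 5.2 matters more because it sits in a primary success criterion.

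**What to change.** **SAP 2.1, after the two listed comparisons, add:** *In addition, one exploratory table will present ZFR00 vs. ZYR00 to support design selection: mean difference (ZFR00 minus ZYR00) with two-sided 95% CI at 1 month, first eyes, for monocular photopic DCIVA, DCNVA and BCDVA, and for monocular log contrast sensitivity at each of the 12 conditions (photopic 3, 6, 12 and 18 cpd; mesopic without glare and mesopic with glare, each at 1.5, 3, 6 and 12 cpd). No success criterion or multiplicity adjustment applies, and no claim of superiority between the lenses will be made.*

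The SAP's 90% intervals for near and distance acuity serve a non-inferiority margin. This contrast has no margin, so 95% is used throughout.

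**Matching edits.** Add a row to SAP Appendix I and adjust the wording on separate comparisons in SAP 1. Make the same adjustment in the Protocol synopsis and Section 20 at the next amendment. Protocol Section 12 requires regulatory and IRB approval for modifications, so the Protocol wording need not hold up the SAP.

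**Minor.** In Protocol 20.6 and SAP 8, the power may be restated as 94% for each lens, and about 90% for both to succeed if each truly gains 1 line; N is unchanged. In SAP 8 and in the SAP 5.2 success criterion, name distance corrected intermediate visual acuity.

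**Cost.** One table, one Appendix I row and a few wording changes, with no added subjects, visits or data. The price is 15 unadjusted intervals of limited precision (42% power for a half-line DCIVA difference), which inform the choice but set no rule for it.

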2.2 VISIT WINDOWS

Subject visits are Preoperative for both eyes; Operative, 1 day and 1 week for each eye; and 1 month and 6 months for both eyes together. The exact number of days for each interval is described in the protocol. The number of eyes with missing visits or data outside of the visit interval will be reported.

2.3 DATA CONVENTIONS

Descriptive statistics will typically include sample size (N), mean, standard deviation (SD), median, minimum (Min.) and maximum (Max.) as appropriate for continuous variables. For categorical data, the frequency and proportion will be computed.

For continuous variables, statistical tests assuming normality will generally be used. However, the data will be reviewed to evaluate whether the normality assumption is appropriate. If it is found not to be appropriate, either an appropriate transformation of the data (i.e., logarithmic) may be used or the corresponding non-parametric tests may be used. Deviations from the proposed statistical guidelines will be substantiated by sound statistical rationale.

Unless otherwise indicated, alpha will be set to 0.05.

For visual acuity data, letter scores will be converted to LogMAR² prior to analysis. Formulas used for visual acuity analyses are included in Appendix II. For refractive data, all values will be converted to plus cylinder with sphere adjusted for infinity³. Formulas used for refractive data are also included in Appendix II.

